Also, initial baseline vital signs (heart rate, blood pressure, respiratory rate, and oxygen saturation) will be obtained. EtCO₂ will be obtained at baseline and periodically using an oral/nasal sample line with the CapnostreamTM 20p monitor (Medtronic, Minneapolis, MN). The study will use a double limb circuit ICU ventilator Puritan BennettTM (Medtronic, Dublin, Ireland).

We will evaluate 4 NIPPV masks (2 oronasal masks and 2 full face masks).

[figure not shown]
Oronasal masks will be labeled as group A and numbered as A1 and A2; while full face masks will be labeled group B and numbered as B1 and B2. Order of the masks will be randomly chosen in two steps. First steps will be choosing A or B then randomly assign mask in each of these groups. We will randomly assign mask in group A or B by drawing an initial mask from the group and then continue the sequence of masks from that point.

For example, we randomly chose group A, then randomly chose A2, the sequence will be A2, A1. Then we would randomly choose B2, then the sequence would be B2, B1.

All subjects will perform 15 minutes on each mask followed by 5 minutes wash out interval between masks. EPAP levels will be 0, 2, 4, & 5 while IPAP remains at 5 higher than EPAP. EtCO₂ will be collected at 4:00, 4:30 and 5:00 minute mark. These three measures should differ by less than 20% of their average. Also, subjective mask

comfort will be assessed via visual analog scale (VAS) with 1 referring to least comfortable and 5 being the most comfortable after 5 each EPAP setting.

Procedure figure:

4- Subject Population:

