4.2. Sample Size

20 healthy subjects.

4.3. Inclusion criteria:

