4.4.2. Facial surgery or deformity

4.4.3. Ear infection

4.4.4. History of pulmonary or cardiac disease

5- Research recruitment and Consent Procedures:

5.1. Subjects will be recruited from students enrolled, faculty, and staff at Rush University.

5.2. An informed consent will be obtained by the investigators for all eligible candidate that meet the criteria.

6- Compensation:

Volunteers will be compensated with \$ 25 Visa gift card

7- Special precautions:

- 7.1. Subjects refrain from eating at least 60 min before the study
- 7.2. Study will be stopped if HR change by 20% from baseline for more than 1 min.
- 7.3. Study will be stopped if subjects complain of shortness of breath

8- Confidentiality:

Subject names, date of birth, and contact information (email) will be stored in REDCap. However, only de-identified data will be used for analysis.

9- Data Collection Instruments/ Data Collection Procedures/Data Analysis Plan:

Data for each subject will be recorded in REDCap

10- Variables:

Dependent: CO₂ clearance, level of comfort-

Independent: NIPPV interface, level of EPAP

11- Limitation:

It is performed on healthy subjects.

12- Analysis:

Data will be recorded in REDCap. Demographics data age (interval), gender (nominal),

ethnicity (nominal) will be collected. HR (continuous), RR (continuous), SpO2

(continuous), ETCO₂ (continuous), EPAP (ordinal), IPAP (ordinal) will be collected.

Means and Standard deviations will be calculated for aforementioned data. NIPPV interfaces number, sizes will be collected. Level of comfort will be collected; median and interquartile ranges will be calculated. Relationship between dependent variable ETCO₂ and independent variable EPAP level will be analyzed by a Kruskal-Wallis test to determine if a significant difference exists. If a significant difference is found a Mann-Whitney U Test will be used to determine which EPAP levels significantly differ. Relationship between dependent variable comfort level and independent variable NIPPV interfaces will be analyzed a Kruskal-Wallis test to determine if a significant difference exists. If a significant difference is found a Mann-Whitney U Test will be used to determine which masks were significantly more comfortable.

Literature cited:

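### The 20% agreement limit on three EtCO₂ readings taken within one minute does not show that EtCO₂ has settled, and unsettled values could bias the EPAP comparison in either direction.

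*Combined protocol and SAP*

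**What the plan says.** Section 3 (Methods) of the combined protocol and SAP fixes the reading times: "EtCO₂ will be collected at 4:00, 4:30 and 5:00 minute mark". The next sentence is the only condition placed on those readings: "These three measures should differ by less than 20% of their average".

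The text does not say:
- whether the limit applies to the largest minus the smallest reading, or to each reading against the average;
- what happens if the limit is exceeded;
- which value (the last reading, the mean or another) enters the analysis.

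The settings are described as "EPAP levels will be 0, 2, 4, & 5 while IPAP remains at 5 higher than EPAP". The text gives no order for the four levels. The procedure figure, which might, is not shown in the text available for this review. On timing, the section says "All subjects will perform 15 minutes on each mask followed by 5 minutes wash out interval between masks".

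Section 12 (Analysis) carries EtCO₂ forward as the CO₂ outcome: "Relationship between dependent variable ETCO₂ and independent variable EPAP level will be analyzed by a Kruskal-Wallis test".

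**The concern.** EtCO₂ is the only CO₂ measure among the collected variables, and the study aim (the EPAP needed to wash out CO₂ with each mask) rests on it. A reading taken a few minutes after a change of mask or pressure represents that setting only if EtCO₂ has stopped moving.

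The agreement sentence is the only place where the plan could establish this. It looks at one minute, allows a wide spread and ignores direction, so three readings in steady climb or steady fall are treated like three readings scattered around a plateau. If settings are read before they settle, each keeps part of the previous setting's level. The contrasts between EPAP levels that Section 12 tests are then distorted, and nothing recorded would show it.

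**Working it through.** **Inputs.** From the documents: readings at 4, 4.5 and 5 min; limit 20% of their average; four EPAP levels; 15 min per mask; "20 healthy subjects". Assumed, because the documents give no values: starting EtCO₂ *B* = 40 mmHg (range 30 to 50 for the limit), total change *D*, time constant *τ* from 1 to 10 min, and reading noise where stated. The 20% figure has no stated derivation, so there is nothing to reproduce.

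**1. Size of the limit.** Largest minus smallest must be below 0.20 × mean: 6, 8 and 10 mmHg at means of 30, 40 and 50. Readings of 36.1, 40.0 and 43.9 pass: the spread is 7.8 and the limit 8.0. If each reading is compared with the average instead, the permitted linear climb at 40 mmHg doubles to 16 mmHg.

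**2. Exponential approach to a new level.** y(t) = B + D(1 − e^(−t/τ)).
- Share of the change falling between 4:00 and 5:00: e^(−4/τ) − e^(−5/τ). It is largest at τ = 1/ln(1.25) = 4.48 min, where it is 0.8⁴ − 0.8⁵ = 0.4096 − 0.3277 = 0.082.
- Share of the change missed by the mean: [e^(−4/τ) + e^(−4.5/τ) + e^(−5/τ)]/3. At τ = 4.48 this is (0.4096 + 0.3664 + 0.3277)/3 = 0.368.

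For B = 40 and D = +10 mmHg:

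| τ (min) | Share of change, 4:00 to 5:00 | Spread as % of mean | 20% rule | Missed by mean | mmHg |
|---|---|---|---|---|---|
| 1 | 1.2% | 0.2% | pass | 1.2% | 0.1 |
| 2 | 5.3% | 1.1% | pass | 10.8% | 1.1 |
| 3 | 7.5% | 1.6% | pass | 22.5% | 2.3 |
| 4.48 | 8.2% | 1.8% | pass | 36.8% | 3.7 |
| 6 | 7.9% | 1.7% | pass | 47.3% | 4.7 |
| 10 | 6.4% | 1.5% | pass | 63.8% | 6.4 |

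With D = +20 the largest spread is about 3.1%. At time constants of 1 to 10 min, no rise up to 2000 mmHg from 35 or 40 mmHg fails. Taking the 5:00 reading alone helps little: it misses e^(−5/τ), or 8%, 33% and 61% at τ = 2, 4.48 and 10.

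**3. Direction.** With D = −10 and τ = 4.48 the rule again passes (spread 2.4%), and the mean is 3.7 mmHg too high.

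**4. Effect on the EPAP contrast.** Illustration: plateaus of 45, 43, 41 and 40 mmHg at EPAP 0, 2, 4 and 5, start at 40, 5 min per level, τ = 4.48.
- Rising order: errors −1.84, +0.13, +0.78 and +0.62 at EPAP 0, 2, 4 and 5. Recorded EPAP 0 minus EPAP 5: (45 − 1.84) − (40 + 0.62) = 2.5, against a true 5.
- Falling order: errors 0.00, −0.37, −0.86 and −1.02 from EPAP 5 down to 0. Recorded contrast: (45 − 1.02) − 40 = 4.0.
- At τ = 1 no error exceeds 0.06 mmHg.

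**5. What the rule responds to.** With an assumed noise SD of 3 mmHg, simulation gives failure in 14.4% of triplets that are settled at 40 mmHg. It gives 7.9% for triplets still rising from 40 towards 50 at τ = 4.48. The rule reacts to scatter, not to drift.

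**6. Tightening the percentage.** A 5% limit still passes every row of the table. It would reject about 33% of settled triplets at a noise SD of 1 mmHg and 76% at 2 mmHg.

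**7. Timing.** Four levels × 5 min = 20 min, against 15 min per mask. 15/4 = 3.75 min per level, which ends before the 4:00 reading.

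**The case against.** The plan never calls the sentence a plateau test. It may be meant only as a repeatability check, and as a screen for gross artefact it is reasonable. That stands, but it leaves the plan with no check on settling. The plan also says "EtCO₂ will be obtained at baseline and periodically using an oral/nasal sample line", so other readings may exist; however, no times or use are given for them.

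A reader might infer that the rule cannot detect a moving EtCO₂ at all. That is too strong: a spread of 8 mmHg or more in the minute, at a mean of 40, fails. Equally, the 7.8 mmHg climb in step 1 shows only how wide the limit is. Under the exponential model it would need a total change of about 95 mmHg (7.8/0.082), and the modelled drifts are far smaller.

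A reader might also infer that rebreathing is systematically understated, to the advantage of low EPAP levels or large masks. The documents do not support this. It requires EtCO₂ to be rising during the reading minute; after a move to a better-clearing level, or under the pressure support itself, it may be falling, and the error reverses. In the rising-order illustration only EPAP 0 is read low. The net direction depends on an order that the text does not give.

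Nor is a material error certain. The documents contain no time constant, and at 1 min the shortfall is about 1%. Finally, a mean that is too low or too high presumes that the three-reading mean is analysed, which the plan does not say.

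**Conclusion.** The concern holds in a limited form. The agreement limit does not demonstrate that EtCO₂ has settled, and nothing else in the text does. Under an assumed exponential approach, the shortfall runs from about 1% of the change (time constant 1 min) to 64% (10 min), and the rule passes throughout, so the trial's own data would not show which case applied. The error can go either way at a given level. In the one illustrative sequence examined, both orders shrank a true 5 mmHg contrast, to about 2.5 or 4.0 mmHg. These sizes rest on the assumed model, starting level, plateaus and time constants; they are a range and not an estimate of bias in this trial. That the rule ignores direction, and its width of 20% of the mean, follow from the text alone.

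**What to change.** 1. Keep a spread limit on the 4:00, 4:30 and 5:00 readings as an artefact check only. State how the spread is computed and what is done when it is exceeded.
2. Record EtCO₂ at 2:00 and 3:00 as well at each setting, from the capnograph already attached.
3. For each mask and EPAP level, estimate the mean within-subject change from 2:00 and from 3:00 to 5:00 across the 20 volunteers, with a confidence interval.
4. Analyse one prespecified EtCO₂ value for every setting, whatever the trend shows.
5. Prespecify a relevant rise. Where the interval does not exclude it, report that level as not shown to be at plateau and do not cite it as evidence of effective washout.
6. State the EPAP order in the text, and reconcile the 15 minutes per mask with four levels each read to 5:00, since this decides whether the reading window exists at every level.

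The trend is better judged across volunteers than setting by setting. An individual limit of, say, 2 mmHg on the 2:00 to 5:00 change would falsely flag about 16% of settled settings at a reading SD of 1 mmHg and 48% at 2 mmHg. It would also never fire on an exponential rise below about 6.1 mmHg. Across 20 volunteers, with independent reading errors and no variation in true change (both assumed), the 95% half-width is 2.093 × √2 × SD/√20, or 0.66 mmHg at SD 1 and 1.32 mmHg at SD 2. Real variation between volunteers would widen it.

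The relevant rise must be set with slow approaches in mind. At a time constant of 10 min, an 8 mmHg rise shows only 1.7 mmHg between 2:00 and 5:00, with 8 × 0.6065 = 4.9 mmHg still to come.

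Cost: two more readings per setting, or 2 × 4 masks × 4 levels = 32 per volunteer, and a short addition to Sections 3 and 12. Some EPAP levels may not be declarable as effective.

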4.1. Population

Normal volunteers from Rush University.

4.2. Sample Size

20 healthy subjects.

4.3. Inclusion criteria:

4.3.1. Age > 18 years' old

4.4 Exclusion criteria:

4.4.1. Prior history of NIPPV as a patient.

4.4.2. Facial surgery or deformity

4.4.3. Ear infection

4.4.4. History of pulmonary or cardiac disease

5- Research recruitment and Consent Procedures:

5.1. Subjects will be recruited from students enrolled, faculty, and staff at Rush University.

5.2. An informed consent will be obtained by the investigators for all eligible candidate that meet the criteria.

6- Compensation:

Volunteers will be compensated with \$ 25 Visa gift card

7- Special precautions:

- 7.1. Subjects refrain from eating at least 60 min before the study
- 7.2. Study will be stopped if HR change by 20% from baseline for more than 1 min.
- 7.3. Study will be stopped if subjects complain of shortness of breath

8- Confidentiality:

Subject names, date of birth, and contact information (email) will be stored in REDCap. However, only de-identified data will be used for analysis.

9- Data Collection Instruments/ Data Collection Procedures/Data Analysis Plan:

Data for each subject will be recorded in REDCap

10- Variables:

Dependent: CO₂ clearance, level of comfort-

Independent: NIPPV interface, level of EPAP

11- Limitation:

It is performed on healthy subjects.

12- Analysis:

Data will be recorded in REDCap. Demographics data age (interval), gender (nominal),

ethnicity (nominal) will be collected. HR (continuous), RR (continuous), SpO2

(continuous), ETCO₂ (continuous), EPAP (ordinal), IPAP (ordinal) will be collected.

Means and Standard deviations will be calculated for aforementioned data. NIPPV interfaces number, sizes will be collected. Level of comfort will be collected; median and interquartile ranges will be calculated. Relationship between dependent variable ETCO₂ and independent variable EPAP level will be analyzed by a Kruskal-Wallis test to determine if a significant difference exists. If a significant difference is found a Mann-Whitney U Test will be used to determine which EPAP levels significantly differ. Relationship between dependent variable comfort level and independent variable NIPPV interfaces will be analyzed a Kruskal-Wallis test to determine if a significant difference exists. If a significant difference is found a Mann-Whitney U Test will be used to determine which masks were significantly more comfortable.

Literature cited:

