Student Research Project Proposal

Title:

Carbon Dioxide (CO₂) Clearance from various face masks in Normal Volunteers at various level of Expiratory Positive Airway Pressure (EPAP) when Using a Non-Invasive Positive Pressure Ventilation (NIPPV)

Investigators:

Mentor:

[name], MHS, RRT, FAARC, FCCP

Graduate Student:

[name], Respiratory Care Department, Rush University.

Study aim:

Determine the EPAP (baseline pressure) required to effectively wash out CO₂ for current available masks, and assess perceived level of comfort with each mask with using noninvasive ventilator.

1- Abstract:

Background: Noninvasive positive pressure ventilation (NIPPV) can be delivered via single limb circuit or double limb circuit ventilators. There are many advantages to NPPV. However, a reasonable number of questions remain unanswered, such as mask impact on carbon dioxide (CO₂) clearance based on EPAP level.

Objective: Determine the EPAP (baseline pressure) required to effectively wash out CO₂ for each mask, and assess perceived level of comfort with each mask with ICU ventilator.

Method: This study will be a randomized crossover trial that will be conducted at Rush University. The study will be conducted with 20 healthy volunteers who will be placed on ICU ventilator operating in the NIPPV mode. All subjects will perform 15 minutes of breathing on NIPPV on each mask of the 4 different masks (2 oronasal and 2 full face masks) that are randomly selected. Breathing through each mask will be followed by a 5-minute wash out period between masks. End tidal Carbon Dioxide (EtCO₂) will be sampled nasal/oral. Different levels of EPAP will be set and CO₂ clearance will be monitored. Additionally, subjective mask comfort will be assessed via visual analog scale (VAS) with 1 referring to least comfortable and 5 being the most comfortable.

2- Introduction

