via EtCO₂. Masks B & C both had higher rate of total leaks due to higher rate of unintentional leaks which may improved CO₂ wash out, hence, led to no differences in PtcCO₂.⁸ Another study compared total face mask against oronasal mask impact on gas exchange (PvCO₂) favors total face mask in the first 6 hours and during the acute phase of respiratory failure using NIPPV.⁷ Both Medrinal and Sadeghi assessed gas exchange not masks' CO₂ clearance. Since the intentional leak impacts CO₂ clearance, and the intentional leak level depends on the level of pressure.⁸ The previous studies didn't study different level of EPAP (baseline pressure). One level of EPAP pressure of 4 cm H₂O was used in Medrinal study based on Samolski's finding.⁸ While in Sadeghi's study, IPAP started at 10 cm H₂O and EPAP started at 4 cm H₂O. IPAP and EPAP were increased gradually based on subjects' need, therefore it lacked consistency in EPAP level.⁹

ICU ventilators using double limb circuit is an alternative to deliver NIPPV, however, researches on minimum baseline pressure required to prevent CO₂ rebreathing is not clear as well. In a study that compared 3 types of masks (2 ONM and 1 FFM) to helmet in acute hypercapnia respiratory failure. NIPPV in both group improved arterial blood gases. ICU ventilators settings in masks group used positive end expiratory pressure (PEEP) referring to baseline pressure that ranged from 3 – 5 cm H₂O (mean 4.26 ± 1.92); and inspiratory pressure adjusted to achieve tidal volume of 6-8 ml/kg (16.37 ± 4.19). On the other hand, settings for helmet groups were ~ 30%.¹¹

The answer regarding effective EPAP level to wash out CO₂ remains uncertain. The purpose of this study is to compare the efficacy of CO₂ clearance between different NIPPV interfaces (oronasal and full face masks) when using double limb circuit ICU

ventilator at lower levels of EPAP. The aim of this study is to determine the EPAP (baseline pressure) required to effectively wash out CO₂ for each mask and assess perceived level of comfort with each mask.

3- Methods:

This study will be a randomized crossover trial that will be conducted at Rush University.

Normal volunteers will be recruited from Rush University Medical Centers. Volunteers will be screened with inclusion and exclusion criteria and an informed consent is required in order for them to participate. Demographic (age, gender, ethnicity) will be obtained.

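### The deciding CO₂ contrast is undefined: the purpose compares masks, the aim is per mask, and the planned EtCO₂ test has no mask factor; no primary endpoint, alpha or multiplicity rule is stated

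*Combined protocol and SAP*

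**What the plan says.** Section 10 (Variables) gives two outcomes, "Dependent: CO₂ clearance, level of comfort", and two factors, "Independent: NIPPV interface, level of EPAP". Neither list is ranked.

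The text states the question in three ways:

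- **Purpose** (last paragraph of the Introduction): "The purpose of this study is to compare the efficacy of CO₂ clearance between different NIPPV interfaces (oronasal and full face masks".
- **Aim** (same paragraph): "The aim of this study is to determine the EPAP (baseline pressure) required to effectively wash out CO₂ for each mask and assess perceived level". The opening Study aim and the abstract's objective ask for the same two things.
- **Analysis** (section 12): "Relationship between dependent variable ETCO₂ and independent variable EPAP level will be analyzed by a Kruskal-Wallis test", and separately "Relationship between dependent variable comfort level and independent variable NIPPV interfaces will be analyzed a Kruskal-Wallis test". Each is followed by Mann-Whitney tests if significant.

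The design in section 3 is a crossover in which every volunteer uses all four masks, with four EPAP levels (0, 2, 4 and 5). Section 4.2 gives 20 volunteers, with no alpha, power or effect size from which a primary comparison could be inferred. Section 12 speaks of significance but states no level, testing order or adjustment.

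**The concern.** A reader of the results needs to know which comparison the trial was set up to make. Once the data are in, at least four could be put forward: EtCO₂ by EPAP pooled over masks, EtCO₂ by EPAP within a particular mask, EtCO₂ by mask, and comfort by mask. They can disagree, and the plan does not say which one counts.

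The larger problem lies inside the CO₂ question. The aim asks for a result mask by mask, because masks may clear CO₂ differently at the same EPAP. A test of EtCO₂ by EPAP that takes no account of mask addresses only the average EPAP effect. If EPAP matters in one mask and not in the others, that test can miss the effect. If it is significant, it does not show in which mask. Per-mask analyses would then be chosen after the fact, with no rule for error across them.

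**Working it through.** **1. Questions set against planned tests**

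| Question | Where stated | Planned test |
|---|---|---|
| CO₂ clearance between masks | Purpose, Introduction | None |
| EPAP required, for each mask | Study aim; abstract; Introduction | None by mask; section 12 tests EtCO₂ by EPAP without mask |
| Comfort with each mask | Study aim; abstract; Introduction | Comfort by mask, section 12 |

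Only the comfort question has a test of the same form as the question.

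**2. Error across the tests that are planned**

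The plan has no error rate or power figure to reproduce. Inputs: two omnibus tests (section 12), and alpha 0.05 per test (assumed, range 0.01 to 0.10).

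For k independent, calibrated tests, P(at least one false positive) = 1 − (1 − α)^k. With k = 2:

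- α = 0.05: 1 − 0.95² = 0.0975
- α = 0.01: 1 − 0.99² = 0.0199
- α = 0.10: 1 − 0.90² = 0.19

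Treating the tests as independent is reasonable here, because one is across EPAP and the other across masks, which are crossed factors. In a null simulation with 20 volunteers, four masks, four EPAP levels and a cell-level residual correlation of 0.8 between EtCO₂ and comfort, the two Friedman statistics correlated about −0.02 and the joint error was 9.8%.

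**3. Error if EtCO₂ is tested separately in each mask**

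Section 12 does not plan this; it follows only if the per-mask aim is carried into the analysis without adjustment. There would be four EtCO₂ tests plus comfort: 1 − 0.95⁵ = 0.226. Correlation lowers it: a Friedman simulation with 20 volunteers and comfort independent gave 20.2% at residual correlation 0.5 and 17.8% at 0.8.

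**4. Error of the unpaired tests as written**

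Kruskal-Wallis treats repeated values from one volunteer as independent. A null simulation (3,000 runs, 20 volunteers, one value per mask and EPAP level, each test at 0.05) used assumed shares of variance:

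| Volunteer share | Volunteer-by-mask share | EtCO₂ by EPAP | Comfort by mask | Either |
|---|---|---|---|---|
| 0 | 0 | 4.7% | 4.7% | 9.1% |
| 0.5 | 0 | 0.3% | 0.6% | 0.9% |
| 0.4 | 0.2 | 0.03% | 9.7% | 9.7% |
| 0.3 | 0.4 | 0.0% | 24.3% | 24.3% |

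The actual rate depends on correlations that the documents do not give. Where volunteers react differently to different masks, the EtCO₂ test becomes very conservative while the comfort test rejects too often.

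**5. Effect of the proposed rule**

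Holm over four masks at overall 0.05 compares the ordered p-values with 0.05/4 = 0.0125, 0.05/3 = 0.0167, 0.05/2 = 0.025 and 0.05. It holds the chance of any false primary claim to at most 5%. Without adjustment, four independent tests would give 1 − 0.95⁴ = 18.5%.

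**The case against.** The strongest reply is that the documents do rank the outcomes in substance. The title concerns CO₂ clearance alone, CO₂ comes first in every statement of the aim, and the abstract brings in comfort as an addition. The two tests use different outcomes and different factors, so a comfort result cannot stand in for an answer about EPAP, and the plan has no rule that either result counts as success. This is also a student project in 20 healthy volunteers, where strict error control over two separate questions can be seen as optional.

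Much of this stands. CO₂ is plainly the leading interest, and a missing label alone would be a small matter. The reply does not settle which CO₂ contrast decides, because the purpose, the aim and section 12 still differ.

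A reader might infer more than the text supports, in three ways:

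- **That each test is run at full alpha.** The plan states no alpha; 0.05 is an assumption.
- **That five omnibus tests are planned, with 22.6% error.** Section 12 plans two. The five-test figure is conditional on separate per-mask testing.
- **That the plan as written inflates false positives.** It may do the opposite: the simulated rate for the two tests runs from 0.9% to 24.3% over the correlated cases shown. That spread comes from ignoring the pairing, which is a separate defect.

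**Conclusion.** The point holds, and its main weight is on the undefined CO₂ contrast. The EtCO₂ test in section 12 does not answer the per-mask aim, the between-mask purpose has no test, and no primary endpoint, alpha or multiplicity rule is given. This conclusion comes from reading the sections together and needs no assumption about correlation or effect size.

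The multiplicity part is modest: about 9.75% for the two planned tests, assuming 0.05 each, independence and calibrated tests. It should not be quoted as the error rate of the analysis as written, which the documents do not allow to be fixed. The change is worth making before data are analysed, because it alters what the trial can conclude and needs no further data.

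**What to change.** In section 12:

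- Name EtCO₂ as the primary endpoint, and EtCO₂ across EPAP levels within each mask as the primary comparison.
- Use a within-volunteer test, for example Friedman in each mask, or a mixed model with mask, EPAP and their interaction from which the per-mask EPAP effects are tested.
- State an overall alpha of 0.05 with Holm adjustment over the four masks. Sidedness need not be given, since it has no meaning for a four-level omnibus test.
- Label comfort by mask as secondary and supportive.
- Either keep the between-mask purpose as a named secondary comparison with its own test (for example the mask and mask-by-EPAP terms), or reword the purpose sentence in the Introduction to match the primary comparison.

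The change of test has to accompany the Holm rule. Adding Holm to unpaired per-mask tests would make them more conservative still: in simulation at within-volunteer correlation 0.5, the null rate of any rejection fell from 1.4% to about 0.05%.

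The cost is a few sentences, with no extra volunteers or measurements. The smallest per-mask p-value must reach 0.0125, and comfort carries no confirmatory claim. If the investigators prefer a different primary contrast, naming it in advance with its alpha and a matching test would also remove the ambiguity, provided the aim is worded to agree.

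### EtCO₂ is summarised and tested only at group level, so an EPAP at which a minority of volunteers rebreathe could be taken as sufficient for a mask

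*Combined protocol and SAP*

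**What the plan says.** The Introduction ends with the objective: "The aim of this study is to determine the EPAP (baseline pressure) required to effectively wash out CO₂ for each mask". The Study aim at the front of the document says much the same. Section 4.2 sets the size at "20 healthy subjects" without a justification.

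Section 3 (Methods) gives the design: "We will evaluate 4 NIPPV masks (2 oronasal masks and 2 full face masks", each worn by every volunteer, with "EPAP levels will be 0, 2, 4, & 5 while IPAP remains at 5 higher than EPAP". EtCO₂ is read three times at each setting. It is also measured before ventilation: "EtCO₂ will be obtained at baseline and periodically using an oral/nasal sample line".

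Section 12 (Analysis) lists EtCO₂ among the continuous variables and states "Means and Standard deviations will be calculated for aforementioned data". EtCO₂ is then compared across EPAP levels by Kruskal-Wallis, with Mann-Whitney tests if that is significant. The only factor named for this test is EPAP; whether it is run per mask or with masks pooled is not stated. The baseline reading does not appear in section 12.

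The only EtCO₂ rule applied to an individual is in section 3: "These three measures should differ by less than 20% of their average". That checks the stability of a reading. It does not define clearance.

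**The concern.** A required EPAP is a threshold. A reader who uses the result will want to know for how many of the 20 volunteers a given EPAP cleared CO₂ with a given mask. A mean, an SD and a test of location between levels do not report that. If most volunteers clear CO₂ and a few do not, the mean moves little and a rank test may show nothing.

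Uneven clearance is plausible on the plan's own account: the Introduction notes that the dead space of full face masks varies between products and that rebreathing can lead to failure of NIPPV. The plan does not say how a flat result will be interpreted. If it is read as adequate clearance, the conclusion for that mask could be falsely reassuring. Each volunteer has an own baseline and readings at every setting, so the missing information can be drawn from data already planned.

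**Working it through.** **Plan's own figure.** The sample size of 20 cannot be reproduced, because no alpha, power, SD or effect size is given. Two-sided alpha 0.05 is assumed below.

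**Inputs from the document.** 20 volunteers; 4 masks; EPAP 0, 2, 4 and 5; three readings per setting; Kruskal-Wallis, then Mann-Whitney.

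**Assumed inputs, not in the document.** Between-volunteer SD 4 mmHg; within-volunteer SD 1.0 to 1.5 mmHg for the value at a setting; a 6 mmHg rise in 4 or 5 of 20 at EPAP 0 only; one mask analysed at a time.

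**1. Shift in the mean.** Shift = rise × k/20. For k = 4: 6 × 4/20 = 1.2 mmHg. For k = 5: 6 × 5/20 = 1.5 mmHg.

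**2. Simulated detection for one mask.**

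| Test | Named in section 12? | Detection, 4-5 of 20 affected |
|---|---|---|
| Kruskal-Wallis over four EPAP levels | Yes | about 0% |
| Friedman over four EPAP levels | No | 11-18% |
| Paired Wilcoxon, EPAP 0 versus 5 | No | 21-32% |
| Paired t-test, EPAP 0 versus 5 | No | 29-61% |

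Repeat runs moved these figures by up to about 3 percentage points. Much of the near-zero rate for Kruskal-Wallis arises because it ignores the pairing within volunteers, which is a separate issue. The paired rows show what remains once that is repaired.

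**3. Planned pairwise test with an unlimited rise.** Suppose a fraction f at one EPAP lies above every reading at the other and the rest do not move. Then U = n²[f + (1−f)/2], with SE = √(n²(2n+1)/12). For n = 20, SE = √(400 × 41/12) = 36.97, and under no difference U = 200.

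- f = 4/20: U = 240, z = 40/36.97 = 1.08, p = 0.28
- f = 5/20: U = 250, z = 50/36.97 = 1.35, p = 0.18
- f = 7/20: U = 270, z = 1.89, p = 0.058
- f = 8/20: U = 280, z = 2.16, p = 0.03

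The expected p-value falls below 0.05 only at 8 of 20, however large the rise.

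**4. Masks pooled (80 readings per EPAP).** In a separate simulation (between SD 3 to 5, within SD 1 mmHg, 4 or 5 of 20 affected at EPAP 0 and 2), Kruskal-Wallis was significant in 0.1-11% of runs for a 3 mmHg rise, 1.5-56% for 5 mmHg and 23-87% for 8 to 10 mmHg. If the same volunteers rebreathed by 5 mmHg at all four levels, the rate was 0%, because levels are compared only with each other.

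**5. What a count would show.** Exact (Clopper-Pearson) 95% limits for the proportion cleared: 20 of 20 gives 83% to 100%; 18 of 20 gives 68% to 99%. Even a clean result leaves a failure rate of up to about 17% (1 in 6) possible.

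**6. Noise in a count.** With within SD 1.5 mmHg at baseline and at the setting, the change has SD √2 × 1.5 = 2.12 mmHg. The false-flag rate per volunteer is 1 − Φ(margin/2.12). The margins are illustrations only.

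- 3 mmHg: 1 − Φ(1.41) = 7.9%. At least one false flag among 20: 1 − 0.921²⁰ = 81% per mask-EPAP cell.
- 5 mmHg: 1 − Φ(2.36) = 0.92%. At least one: 1 − 0.9908²⁰ = 17% per cell. A true 6 mmHg rise is missed with probability Φ((5−6)/2.12) = 32%.

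Expected flags at 5 mmHg with 4 true rebreathers: 4 × 0.68 + 16 × 0.0092 = 2.9, against 20 × 0.0092 = 0.2 with none. The count separates these cases on average, but does not classify each person reliably.

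**The case against.** **The individual threshold is an interpretation.** The aim is worded per mask, and the Introduction also states a purpose of comparing clearance between interfaces. A group comparison is a legitimate answer to that. This stands, and is why the count should complement the group analysis and not replace it.

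**The more basic gap is the missing definition of effective washout.** This also stands. Reading a flat result as sufficient is an assumption about how the results will be used; the plan has no rule for it or against it. The proposed count needs a margin that the plan does not yet have.

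**A reader might infer that the plan will pass an EPAP that fails a fifth to a quarter of wearers.** The document does not support that. It gives no rebreathing rate, rise or SD; 4 to 5 of 20 is an illustration.

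**A reader might also infer that any comparison of means would hide the minority.** That is too strong. In the assumed scenario a paired t-test detects it in 29-61% of trials, and in more than half when 5 of 20 are affected and the within SD is 1.0 mmHg. Section 12, however, names unpaired rank tests.

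**Pooling would help detection.** With large rises it often would, as step 4 shows, but a pooled test cannot give an EPAP for each mask.

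**Counts are noisy.** This stands and is more than a footnote, given an 81% chance of at least one false flag per cell at a 3 mmHg margin. In addition, the pre-ventilation baseline is unassisted, while every setting adds IPAP 5 above EPAP. A change from baseline may therefore partly reflect the pressure support itself.

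**Conclusion.** The concern holds in a limited form. Section 12 cannot show how many volunteers an EPAP fails to clear for a given mask. If a flat or non-significant result is taken as adequate clearance, an EPAP at which a minority rebreathe could be called sufficient. For one mask under the assumed values, the planned omnibus test has almost no chance of signalling a 6 mmHg rise in 4 or 5 of 20, and rank tests that respect the pairing find it in at most about a third of trials. The detection percentages rest on the assumed SDs, rise and pattern. The absence of any individual-level result does not. The document does not establish that such a minority exists or that the investigators would misread a flat result. This is a worthwhile, inexpensive improvement to the analysis plan and does not invalidate the design.

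**What to change.** Add to section 12, alongside the group analysis:

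1. For each mask and EPAP, tabulate each volunteer's change: the mean of the three readings minus own baseline.
2. Report the number of 20 whose rise exceeds a margin that the investigators choose and justify before data collection, with an exact 95% CI. Show the count at a few other margins.
3. State each mask's EPAP conclusion together with the proportion of volunteers cleared and its lower confidence limit.
4. State the limits: reading noise misclassifies individuals; isolated flags and the largest single rise should not be over-read; the exact CI does not cover this error; and a change from unassisted baseline may partly reflect the pressure support.

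The cost is a few sentences and one table. No measurement or visit is added. The real work is agreeing the margin in advance, which a definition of effective washout would need in any case. A lower margin raises false flags and a higher one misses more true rises, which is the reason for showing several.
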